6.2.3 End of trial and follow-up period

For AE assessment, laboratory tests, recording of ECG and vital signs, and physical examination during the end of trial period, see [Sections 5.2.2](#) to 5.2.5.

Subjects who discontinue treatment before the end of the planned treatment period should visit the trial site undergo the examination to check the subject's safety where applicable, and then undergo the EOT examination 5 to 14 days after the day of last treatment.

All abnormal values (including laboratory parameters) that are considered clinically relevant by the investigator will be monitored using the appropriate tests until a return to a medically acceptable level is achieved. (S)AEs persisting after subject's end of trial must be followed up until they have resolved, have been sufficiently characterised, or no further information can be obtained.

The end of the trial as a whole is defined by the 'last regular visit completed by last subject' or 'end date of the last open AE' or 'date of the last follow-up test' or 'date of an AE has been decided as sufficiently followed-up', whichever is latest.

7. STATISTICAL METHODS AND DETERMINATION OF SAMPLE SIZE

7.1 STATISTICAL DESIGN – MODEL

7.1.1 Objectives

The primary objective of this trial is to establish the bioequivalence of tablet formulation of 110 mg DE compared to commercial capsule formulation following oral administration under fasted condition. The trial is designed to allow intra-subject comparisons and will be evaluated statistically by use of an appropriate linear model.

The secondary objective is the evaluation and comparison of several pharmacokinetic parameters between the treatments. The secondary objective(s) will be assessed by descriptive statistics.

The assessment of safety and tolerability will be an additional objective of this trial, and will be evaluated by descriptive statistics.

7.1.2 Endpoints

Bioequivalence is to be determined on the basis of the primary endpoints (see [Section 5.5.1](#)).

Safety and tolerability will be determined on the basis of the parameters specified in [Section 5.2.1](#).

7.1.3 Model

The statistical model used for the analysis of primary and secondary endpoints will be an ANOVA (analysis of variance) model on the logarithmic scale. This model will include effects accounting for the following sources of variation: ‘sequence’, ‘subjects within sequences’, ‘period’ and ‘treatment’. The effect ‘subjects within sequences’ will be considered as random, whereas the other effects will be considered as fixed. The model is described by the following equation:

$$y_{ijkm} = \mu + \zeta_i + s_{im} + \pi_j + \tau_k + e_{ijkm}, \text{ where}$$

y_{ijkm} = logarithm of response (endpoint, see [Section 5.5.1](#)) measured on subject m in sequence i receiving treatment k in period j,

μ = the overall mean,

ζ_i = the ith sequence effect, $i = 1, 2$

s_{im} = the effect associated with the mth subject in the ith sequence,
 $m = 1, 2, \dots, 80$

π_j = the jth period effect, $j = 1, 2, 3, 4$

τ_k = the kth treatment effect, $k = 1, 2$,

e_{ijkm} = the random error associated with the mth subject in sequence i who received treatment k in period j .

It is assumed that random errors were normally distributed and different formulation can have different variability, that is $e_{ijkm} \sim N(0, \sigma_k^2)$.

7.2 NULL AND ALTERNATIVE HYPOTHESES

The assessment of bioequivalence will be based upon two-sided 90% confidence intervals (CIs) for the ratio of the geometric means (test/reference) for the primary and secondary endpoints using an acceptance range of 80.0-125.0%. This method is equivalent to the two one-sided t-tests procedure, each at the 5% significance level (on the log scale).

In general, the hypothesis of inequivalence is tested:

Null hypothesis H_0 (Inequivalence): $\mu_T - \mu_R \leq -\delta$ or $\mu_T - \mu_R \geq \delta$

where μ_T and μ_R are the means of the log-transformed endpoint for the test and reference treatments, respectively, and δ is the bioequivalence limit that defines the acceptance range on the logarithmic scale.

Thus the null hypothesis is that the difference of the population average responses is either less than or equal to the lower bound or greater than or equal to the upper bound of the acceptance range.

Alternative hypothesis H_a (Equivalence): $-\delta < \mu_T - \mu_R < \delta$

i.e. the difference of the population average responses is both greater than the lower bound and less than the upper bound of the acceptance range.

In this trial, the bioequivalence limit δ is $\ln(1.25)$. By back-transforming (exponentiating), this translates to an acceptance range of 80.00 to 125.00% for the ratio of the geometric means (test/reference) for endpoints on the original (linear) scale.

The above null hypothesis H_0 of inequivalence and its alternative H_a can be decomposed into two one-sided null hypotheses, H_{01} and H_{02} , with their accompanying alternatives:

H_{01} : $\mu_T - \mu_R \leq -\delta$ vs. H_{a1} : $\mu_T - \mu_R > -\delta$

H_{02} : $\mu_T - \mu_R \geq \delta$ vs. H_{a2} : $\mu_T - \mu_R < \delta$

Due to the nature of normal-theory confidence intervals, the test of the null hypothesis H_0 at the level of significance of $\alpha = 0.05$ is equivalent to carrying out two one-sided tests of the above null hypotheses H_{01} and H_{02} each at the level of significance of $\alpha = 0.05$. The rejection

of both null hypotheses at the $\alpha = 0.05$ level is equivalent to the inclusion of the 90% confidence interval for $\mu_T - \mu_R$ in the acceptance range $(-\delta, \delta)$.

7.3 PLANNED ANALYSES

7.3.1 Primary analyses

The pharmacokinetic endpoints listed in [Section 5.5.1](#) will be calculated according to the BI SOP 'Standards and processes for analyses performed within Clinical Pharmacokinetics/Pharmacodynamics' ([001-MCS-36-472](#)).

Pharmacokinetic parameters of a subject will be included in the analysis unless the subject has an important protocol violation relevant for the evaluation. Whether a protocol violation is important will be decided no later than in the Report Planning Meeting.

Reasons for exclusion of single pharmacokinetic parameters may be:

- The subject experiences emesis at or before two times median t_{max} . Median t_{max} is to be taken either from the median t_{max} for the reference product or from median t_{max} for the test product, depending on whether the subject had experienced emesis after taken the test or the reference product. Median t_{max} is to be determined excluding the subjects experiencing emesis.
- Time deviations
- Use of restricted medications
- A pre-dose concentration is $>5\%$ of the C_{max} value of that subject

The subject set for the evaluation of PK endpoints (PK parameter analysis set [PKS]) will include all treated subjects that provide at least one observation for at least one primary endpoint without important protocol violations with respect to the statistical evaluation of PK endpoints. It will also be decided in the Report Planning Meeting which subjects are to be included in the PKS.

Point estimates of bioavailability, the ratios of the geometric means (test/reference) for the primary and secondary endpoints (see [5.5.1.1](#), [5.5.1.2](#)), and their two-sided 90% confidence intervals (CIs) will be provided.

To this end, the PK endpoints will be log transformed (natural logarithm) prior to fitting the ANOVA model (cf. [Section 7.1.3](#)). For each endpoint, the difference between the expected means for $\log(T)$ - $\log(R)$ will be estimated by the difference in the corresponding adjusted means (LeastSquares Means), and a two-sided 90% confidence interval based on the t-distribution will be computed. These quantities will then be back-transformed to the original scale to provide the point estimate and 90% CIs for each endpoint.

Bioequivalence is considered established if the 90% confidence intervals of both ratios of the geometric means for the primary endpoints (see [Section 5.5.1.1](#)) are contained in the pre-defined acceptance range (see [Section 7.2](#)). Therefore, no adjustment of the level of significance is necessary.

7.3.2 Secondary analyses

The secondary parameters (refer to [Section 5.5.1](#)) will be calculated according to the BI SOP ‘Standards and processes for analyses performed within Clinical Pharmacokinetics/ Pharmacodynamics’ ([001-MCS-36-472](#)) and will statistically be assessed using the same methods as described for the primary endpoints. $AUC_{0-\infty}$ will be calculated using the $AUC_{0-\infty}$ based on observed and predicted last concentrations, and for statistical analysis, $AUC_{0-\infty}$ based on both observed and predicted last concentrations will be used.

[REDACTED]

7.3.4 Safety analyses

Safety will be assessed for the endpoints listed in [Section 5.2.1](#). All treated subjects (that is, all subjects who received at least one dose of trial drug), will be included in the safety analysis. Safety analyses will be descriptive in nature and will be based on BI standards. No hypothesis testing is planned.

The analyses will be done by ‘treatment at onset’.

Treatments will be compared in a descriptive way. Tabulations of frequencies/proportions will be used for the evaluation of categorical (qualitative) data, and tabulations of descriptive statistics will be used to analyse continuous (quantitative) data.

Measurements (such as ECG, vital signs, or laboratory parameters) or AEs will be assigned to treatments (see [Section 4.1](#)) based on the actual treatment at the planned time of the measurement or on the recorded time of AE onset (concept of treatment emergent AEs).

Therefore, measurements planned or AEs recorded prior to first intake of trial medication will be assigned to 'screening', those between first trial medication intake until end of the residual effect period (see [5.2.2.2](#)) will be assigned to the treatment period. Events after the residual effect period but prior to next intake or end of trial examination will be summarized as 'post-treatment', those after the end of trial examination will be assigned to 'post-trial'. These assignments including the corresponding time intervals will be defined in detail in the TSAP.

Adverse events will be coded using the Medical Dictionary for Regulatory Activities. Frequency, severity and causal relationship of AEs will be tabulated by treatment, system organ class and preferred term. SAEs and other significant AEs (according to ICH E3) will be listed separately.

Laboratory data will be compared to their reference ranges. Values outside the reference range as well as values defined as clinically relevant will be highlighted in the listings. Additionally, differences from baseline will be evaluated.

Vital signs or other safety-relevant data observed at screening, baseline, during the course of the trial and at the end-of-trial evaluation will be assessed with regard to possible changes compared to findings before start of treatment.

Relevant ECG findings will be reported as AEs.

7.3.5 Interim analyses

No interim analysis is planned.

7.3.6 Pharmacokinetic analyses

The pharmacokinetic parameters listed in [Section 5.5.1](#) for DE will be calculated according to the relevant SOP of the Sponsor ([001-MCS-36-472](#)). Pharmacokinetic analyses will be performed using validated software programs, normally, Phoenix Winnonlin (Pharsight®) with applications validated for the respective purpose. Graphs and tables will be generated using validated customised SAS® macros or appropriate graphic software. A reference to the software used, e.g., name, will be indicated in the clinical trial report.

Subjects who are not included in the PKS (refer to [Section 7.3.1](#).) will be reported with their individual plasma concentrations and individual pharmacokinetic parameters; however, they will not be included in descriptive statistics for plasma concentrations, pharmacokinetic parameters or other statistical assessment.

Only concentration values within the validated concentration range and actual sampling times will be used for the calculation of pharmacokinetic parameters. Concentrations used in the

pharmacokinetic calculations will be in the same format provided in the bioanalytical report, (that is, to the same number of decimal places provided in the bioanalytical report).

If a predose concentration value is greater than 5% of C_{max} , the subject's pharmacokinetic data will be not included in any statistical evaluations, in accordance with international guidances. The individual pharmacokinetic parameters of such a subject will be calculated and listed separately. If a predose concentration is above BLQ (below limit of quantification), but less than or equal to 5% of the subject's C_{max} value, the subject's data without any adjustments will be included in all pharmacokinetic measurements and calculations.

7.4 HANDLING OF MISSING DATA

7.4.1 Safety

With respect to safety evaluations, it is not planned to impute missing values.

7.4.2 Plasma drug concentration - time profiles

Handling of missing PK data will be performed according to the relevant Corporate Procedure of the Sponsor ([001-MCS-36-472](#)).

Drug concentration data identified with no sample available (NOS), no valid result (NOR), not analysed (NOA), BLQ, or no peak detectable (NOP) will be displayed as such and not replaced by zero at any time point (this rule also applies also to the lag phase, including the predose values).

7.4.3 Pharmacokinetic parameters

Handling of missing PK data will be performed according to the relevant SOP of the Sponsor (001-MCS-36-472).

For the non-compartmental analysis, concentration data identified with NOS, NOR or NOA will generally not be considered. Concentration values in the lag phase identified as BLQ or NOP will be set to zero. All other BLQ/NOP values of the profile will be ignored. The lag phase is defined as the period between time zero and the first time point with a concentration above the quantification limit.

7.5 RANDOMISATION

Subjects will be randomised to one of the two treatment sequences in a 1:1 ratio.

The sponsor will arrange for the randomisation as well as packaging and labelling of trial medication. The randomisation list will be generated using a validated system, which involves a pseudo-random number generator and a supplied seed number so that the resulting allocation is both reproducible and non-predictable.

The randomisation list will contain additional blocks to allow for subject replacement (refer to [3.3.5](#)).

7.6 DETERMINATION OF SAMPLE SIZE

The sample size for the trial was determined assuming a geometric mean of 110% (tablet/capsule) and an intra-subject coefficient of variation (gCV) of 70% for AUC or C_{max} based on the following possible scenarios. The gCV for capsule formulation were observed as 49.67% for C_{max} and 49.83% for AUC in trial 1160.117*. The gCV for tablet formulation were observed as 62.9% for C_{max} and 69.3% for AUC in trial 1160.246. The Geometric mean ratio of AUC and C_{max} was observed as 1.08 (tablet/capsule) in trial 1160.246.

Since both endpoints of tablet and capsule formulations are highly variable, possible outcome scenarios are conservatively assumed to detect possible bioequivalence. It is assumed that gCV for both formulations can be variable from 50% to 70% as observed in gCV for test formulation in further analysis of the pilot BA study of 1160.246 and geometric mean ratio can be increased from 1.08 to 1.10.

Based on the scenarios and the sample size of 160, the power to reject the null hypothesis of bio-inequivalence for one parameter (for AUC or C_{max}) in favour of equivalence at the 5% level of significance is displayed in Table 7.6: 1 under various assumptions for the intra-subject ratio.

Table 7.6: 1 Power for concluding bioequivalence in a replicate design crossover trial (N=160) based on a geometric mean of 110% and a geometric coefficient of variation of 70% and an acceptance range of 80-125% for different expected ratios of means (tablet/capsule) and gCVs

Given Sample Size 160		Possible gCV		
		0.5	0.6	0.7
Possible Geometric mean ratio	1.08	98.8%	94.3%	89.2%
	1.09	98.4%	93.9%	86.9%
	1.1	94.7%	90.8%	81.7%

1) Ratio of the geometric means (tablet/capsule) for a PK endpoint defined by $\exp(\mu T)/\exp(\mu R)$ (cf. [Section 7.2](#))

From Table 7.6:1, a sample size of 152 will have at least 80% power to conclude bioequivalence if the ratio is between 108% and 110%, that is not more than 10% different from the ratio of 100% that reflects perfect equivalence and the gCV is between 50% and 70%. 160 subjects should be recruited in the trial.

If bioequivalence cannot be demonstrated because of an insufficient sample size, an extension of the trial can be performed by adding not less than half the number of subjects in the initial trial.

The calculation was performed as described by Diletti et al [[R94-1445](#)] using SAS 9.4..

*Trial 1160.117 is an open-label, randomised, single dose, replicate design in a two treatments, four periods crossover phase I study to compare two different capsule formulations of dabigatran etexilate and its sample size was 180 subjects. The true gCVs of its reference capsule formulation are assumed to be identical to those of the capsule formulation used in this study.

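### Section 7.6 gives the power for one endpoint as the power to conclude bioequivalence; at the plan's sizing scenario the chance that both endpoints pass is 64–80% with 152 subjects

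*Protocol*

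**What the plan says.** - Protocol 7.6 sizes the trial on a tablet/capsule ratio of 110% and an intra-subject gCV of 70%. On variability it says: "It is assumed that gCV for both formulations can be variable from 50% to 70" per cent.
- Protocol 7.6 introduces Table 7.6:1 as "the power to reject the null hypothesis of bio-inequivalence for one parameter", AUC or Cmax. The table is headed "Given Sample Size 160" and gives 81.7% at ratio 1.10, gCV 0.7. Its title nevertheless describes the contents as power for concluding bioequivalence.
- Protocol 7.6 then concludes, citing that table, that "a sample size of 152 will have at least 80% power to conclude bioequivalence if the ratio is between 108% and 110" per cent and the gCV is 50–70%. It asks for 160 subjects to be recruited.
- Protocol 7.3.1 sets the success rule: "Bioequivalence is considered established if the 90% confidence intervals of both ratios of the geometric means for the primary endpoints" lie inside the acceptance range. Section 5.5.1.1 names the two endpoints, AUC0-tz and Cmax of free dabigatran.
- SAP sections 7.4 and 7.5 refer back to the protocol for the analysis. Neither document gives a joint power or a correlation between the two endpoints.

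**The concern.** The concluding sentence drops the one-parameter qualifier and uses the phrase that section 7.3.1 reserves for both endpoints passing. A reader will take 80% as the chance that the trial succeeds by its own rule. When two endpoints must both pass, that chance cannot exceed the lower of the two single-endpoint powers, and it falls below it unless the estimates are almost perfectly correlated. Section 7.3.1 correctly notes that no adjustment of the significance level is needed, but that concerns the type I error and says nothing about power.

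What is at stake is the stated risk of an inconclusive trial, and hence how often the extension allowed in section 7.6 might come into play. The risk of a false bioequivalence claim is not affected.

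There is also a traceability gap: the figure of 152 is attributed to a table computed for 160.

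**Working it through.** **Inputs.** One-sided α = 0.05 for each test and limits ±ln(1.25) (Protocol 7.2); sequences TRRT/RTTR (3.1), allocated 1:1 (7.5); ratio and gCV scenarios and N = 152 or 160 (7.6). The correlation ρ between the two log-ratio estimates is an assumption, varied from 0 to 1.

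**Formulas.** Within-subject variance σ² = ln(1 + CV²). Each subject receives each formulation twice, so var(T − R) = (σ_T² + σ_R²)/(2N), which is σ²/N when both formulations share one gCV. Residual df = 3N − 4. Per-endpoint power is close to Φ(a), with a = (ln 1.25 − ln ratio)/SE − t(0.95, df); the lower limit contributes almost nothing at these ratios. The figures below integrate over the distribution of the residual variance.

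**Step 1: reproduce the plan.** For ratio 1.10 and gCV 70%, σ² = ln(1.49) = 0.3988 and ln 1.25 − ln 1.10 = 0.1278.
- N = 160: SE = √(0.3988/160) = 0.0499; a = 2.561 − 1.648 = 0.913; power 81.9% (Table 7.6:1 has 81.7%).
- N = 152: SE = √(0.3988/152) = 0.0512; a = 2.496 − 1.648 = 0.848; power 80.2%.

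All nine cells of Table 7.6:1 agree to within 1.5 percentage points. The 80% at 152 subjects is therefore correct as a single-endpoint figure.

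**Step 2: require both endpoints.** With the same ratio and gCV for both endpoints, joint power is the bivariate normal probability that both tests pass. At ρ = 0 it is the square of the single-endpoint power (0.8015² ≈ 0.64). A simulation with a correlated residual matrix gives the same values to within 0.1 point.

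| ρ (assumed) | N = 152 | N = 160 |
|---|---|---|
| 0 | 64.3% | 67.1% |
| 0.5 | 68.9% | 71.4% |
| 0.8 | 73.1% | 75.3% |
| 0.9 | 75.2% | 77.2% |
| 0.95 | 76.6% | 78.6% |
| 1 | 80.2% | 81.9% |

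At N = 160 joint power reaches 80% only from about ρ = 0.985 (79.8% at 0.98, 80.4% at 0.99).

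**Step 3: the rest of the grid at N = 152.**

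| Ratio, gCV | Per endpoint | Joint, ρ = 0 | Joint, higher ρ |
|---|---|---|---|
| 1.09, 70% | 84.7% | 71.8% | 78.8% (0.8), 80.5% (0.9) |
| 1.08, 70% | 88.6% | 78.5% | 81.1% (0.5) |
| 1.10, 60% | 88.4% | 78.1% | 80.8% (0.5) |

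The other five cells are at least 84% at any ρ from 0 to 1, and at gCV 50% at least 91%.

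**Step 4: observed gCVs by formulation.** Section 7.6 reports 62.9% (Cmax) and 69.3% (AUC) for the tablet, and 49.67% and 49.83% for the capsule. For the capsule it adds: "The true gCVs of its reference capsule formulation are assumed to be identical to those of the capsule formulation used in this study".
- AUC: mean variance (0.3922 + 0.2218)/2 = 0.3070, equivalent to a common gCV of 59.9%.
- Cmax: mean variance (0.3334 + 0.2205)/2 = 0.2769, equivalent to 56.5%.

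At N = 152 and ratio 1.10, power is 88.4% for AUC and 91.1% for Cmax. Joint power is 0.884 × 0.911 = 80.5% at ρ = 0, rising to 88.4% at ρ = 1.

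**The case against.** The strongest reply is that the scope is disclosed. Section 7.6 says the table covers one parameter, the table's footnote refers to a single PK endpoint, and the criticised sentence opens by pointing to that table. On this reading only a qualifier is missing and no number is wrong. It is true that no number is wrong. But the sentence uses the phrase that section 7.3.1 defines as both endpoints passing, and it is the sentence a reader will carry away.

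The second reply is that 64% is unrealistic, since both endpoints come from the same concentration profile and should be positively correlated. That is reasonable, and for that reason the low end should not be quoted alone. It does not rescue the claim: at an assumed 0.95, joint power is still below 80% with 152 or with 160 subjects.

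The third reply is that the scenario is pessimistic and that 160 subjects are recruited, with replacement possible under section 3.3.5. This has force. At N = 160, seven of the nine cells reach 80% even at ρ = 0, and from ρ = 0.8 only the corner cell falls short. The corner is nevertheless the scenario on which the plan says it sized the trial, and it lies inside the range for which at least 80% is asserted.

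Last, the extension provision could raise the eventual chance of success. The documents do not allow that effect to be quantified, and it does not make the statement about the initial 152 subjects correct.

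**Conclusion.** The concern holds. The per-endpoint power is correct, but the unqualified statement of at least 80% power to conclude bioequivalence is not supported at ratio 1.10 and gCV 70%. There the chance that both endpoints pass with 152 subjects is 64–80% over correlations 0 to 1, and 73–77% for correlations of 0.8 to 0.95. This rests on the same ratio and gCV for both endpoints, the same gCV for both formulations, and a non-negative correlation that the documents do not supply.

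The overstatement is confined mainly to the high-gCV, high-ratio end of the grid. If the capsule gCV is near 50%, as observed, joint power is above 80% even at ratio 1.10 and zero correlation. The finding is therefore an overstated trial-level power. It does not show that the trial is underpowered across its planning range, and the error rate and decision rule are unaffected.

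**What to change.** In Protocol 7.6:

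1. Label the 80% sentence and the title of Table 7.6:1 as power per primary endpoint.
2. Add the probability that both primary endpoints pass, over a stated range of assumed correlations. At ratio 110% and gCV 70% this is 64% (correlation 0) to 80% (correlation 1) for 152 subjects, and 67% to 82% for 160. With the observed formulation-specific gCVs at ratio 110% it is 80.5% to 88.4% for 152.
3. Show the per-endpoint values for 152 beside those for 160 (for example 80.2% and 81.9% at ratio 1.10, gCV 70%), or cite the calculation that produced 152.

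The cost is one paragraph, one table title and, if the 152 values are tabulated, extra table entries. The stated power at the worst-case corner becomes less favourable. Enrolment, analysis and decision rule do not change.
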